9.1.2 Sensitivity Analysis

Two sensitivity analyses will be performed for the primary efficacy endpoint.

9.1.2.1 Observed Cases (OC) Analysis

The first sensitivity analysis will include all available assessments of Hb responder and will not exploit imputation of missing Hb responder status (i.e., only Observed Cases [OC] of Hb responder status are considered here). The primary efficacy endpoint analysis will be repeated using the OC approach for the ITT and PP populations. The proportion of Hb responders at Week 12 (OC) will be summarised using descriptive statistics for each treatment arm and overall. The summary will include the corresponding logistic regression model adjusted difference in the proportions of Hb responders (risk difference) between the two treatment arms, the adjusted 95% CI for the difference in proportions, and the adjusted p-value from testing the null hypothesis of inferiority in risk difference with non-inferiority margin 20%. The summary will also include the estimated adjusted odds ratio of Hb responder at Week 12 (OC) between the two treatment arms and corresponding 95% CI for the odds ratio.

9.1.2.2 Observed Cases (OC) Repeated Measures Analysis

The second sensitivity analysis for the primary efficacy endpoint will be performed on the ITT and PP populations, in which Hb responder status will be analysed in a longitudinal analysis using a repeated measures generalized linear mixed model (GLMM) approach (i.e., a repeated measures logistic regression approach) for all available assessments of Hb (i.e., only Observed Cases [OC] of Hb responder status are considered here) over Visits 2 (Day 0; baseline) to 4 (Week 12). The approach will fit a logistic model to the Hb responder dependent variable, where an unstructured working correlation structure will be specified (e.g., by way of the appropriate random statement within the GLIMMIX SAS® procedure) to model the within-subjects correlation of repeated Hb responder status at Visits 3 and 4. If the model fit fails to converge, alternative working correlation structures will be examined. Covariates of the GLMM will include the fixed effects of treatment, baseline Hb, IBD subgroup, visit, and treatment-by-visit interaction. The estimated adjusted odds ratio for treatment effect, and its corresponding 95% CI, from the

model will be presented by visit.

To assess the sensitivity of Hb responder status over time – by way of a general linear model (GLM) approach – separate logistic regression models will be fitted to the Hb responder dependent variable at each visit during the Treatment Period up to Week 12, using all available assessments of Hb (i.e., only Observed Cases [OC] of Hb responder status are considered here). Each model will include terms for the effects of treatment, baseline Hb (below the observed median or at least the observed median), and IBD subgroup. The estimated adjusted odds ratio for treatment effect, and its corresponding 95% CI, will be presented for each model (i.e., by visit). Sensitivity of Hb responder status over time will be assessed by comparing these by-visit treatment effect odds ratio estimates from the logistic regression models (the GLMs) to those obtained from the GLMM model.

9.2 Secondary Efficacy Analyses

9.2.1 Secondary Analysis

9.2.1.1 Key Secondary Endpoints

The change from baseline (CFB) in Hb concentration at Week 12 (MI) secondary endpoint will be analysed for the ITT population using an analysis of covariance (ANCOVA) model.

For the multiple imputation, the code for implementing the SAS® procedure MIANALYZE to the CFB Hb concentration at Week 12 secondary endpoint is:

```
DATA CFB_Impute; SET MI_out; CFBHbW12 = Week12Hb - baselineHb; RUN;
```

```
PROC SORT DATA = CFB_Impute; BY _Imputation_; RUN;
```

```
PROC REG DATA = CFB_Impute OUTEST = outreg COVOUT;  
  BY _Imputation_;  
  MODEL CFBHbW12 = binarybaselineHb TreatmentArm IBDGroup;  
RUN;
```

```
PROC MIANALYZE DATA = outreg EDF = <complete-data degrees of freedom>;  
  MODELEFFECTS Intercept binarybaselineHb TreatmentArm IBDGroup;  
  ODS OUTPUT ParameterEstimates = parm1;  
RUN;
```

The ANCOVA model will have terms for treatment arm, baseline Hb (below the observed median or at least the observed median), and IBD subgroup. The treatment effect of ferric maltol compared to IV Iron will be considered using differences of adjusted means. No formal statistical significance level in the treatment comparison will be defined, as the p-value from the ANCOVA model will be presented for descriptive purposes only. A summary of CFB in Hb concentration (OC) will be provided using descriptive statistics for each visit over the Treatment Period by treatment arm and overall. The summary will include the following

ANCOVA model estimates: adjusted means (i.e., Least-Square Means [LSMs]) of CFB in Hb concentration at Week 12 for each treatment arm, the difference in treatment arm LSMs, the corresponding 95% CIs for treatment arm specific LSMs and difference in treatment arm LSMs, and the p-value for the difference in treatment arm LSMs. Mean CFB in Hb concentration will be plotted against visit (OC) by treatment arm for the ITT and PP populations.

A dichotomous variable, representing status of Hb concentration relative to the normal limits of Hb will be calculated for each visit over the Treatment Period. Women with Hb concentration greater than 12 g/dL and men with Hb concentration greater than 13 g/dL will be classified to be within normal limits of Hb. Those subjects with Hb concentration within the normal limits will be classified as "Hb normal limit responders". Subjects missing Hb concentration at Week 12 will be assumed to have Hb concentration not within normal limits (i.e., these subjects will be considered Hb normal limit non-responders). The logistic regression modelling and hypothesis testing for the primary analysis (Section 9.1.1) will be repeated here for the Hb normal limit responder at Week 12 secondary endpoint.

The code for implementing the SAS® procedure MIANALYZE to the Hb normal limit responder at Week 12 secondary endpoint for the ITT population is:

```
DATA NormalHb_Impute; SET MI_out;
  NLResponder = 0;
  IF Gender =: 'F' AND Week12Hb > 12.0 THEN NLResponder = 1;
  IF Gender =: 'M' AND Week12Hb > 13.0 THEN NLResponder = 1;
RUN;

PROC SORT DATA = NormalHb_Impute; BY _Imputation_; RUN;

PROC LOGISTIC DATA = NormalHb_Impute;
  MODEL NLResponder = binarybaselineHb TreatmentArm IBDGroup / covb;
  BY _Imputation_;
  ODS OUTPUT ParameterEstimates = lgsparms
               CovB              = lgscovb;
RUN;

PROC MIANALYZE PARMS = lgsparms COVB(effectvar=stacking) = lgscovb;
  MODELEFFECTS Intercept binarybaselineHb TreatmentArm IBDGroup;
RUN
```

A summary will be provided for the Hb normal limit responder secondary endpoint using descriptive statistics by visit over the Treatment Period for each treatment arm and overall, utilizing all available Hb data (i.e., OC approach). The summary will also present the Hb normal limit responder rate for the Week 12 visit (MI) for ITT population using descriptive statistics, and will include the corresponding logistic regression model adjusted difference in proportions of Hb normal limit responders between the two treatment arms, the corresponding [Delta Method derived] adjusted 95% CI for the difference in proportions, and the p-value from testing the null hypothesis of inferiority in risk difference with non-inferiority margin 20%. Finally, the summary will also present the estimated logistic regression model adjusted odds ratio of Hb normal limit responders at Week 12 (MI) between

the two treatment arms and corresponding 95% CI for the odds ratio.

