3 STUDY DESIGN

3.1 Overall Study Design

This study will be a Phase 3b, multicentre, open-label, active-controlled, randomized, parallel group prospective study to compare the efficacy and safety of ferric maltol to IV Iron in subjects with inflammatory bowel disease. A total of 242 subjects from 35-45 European sites and around 18 United States sites will be randomized at a ratio of 1:1 to the two treatment arms of this study.

The randomization will be stratified according to screening Hb (<10g/dL or ≥ 10g/dL for Female; < 11g/dL or ≥ 11g/dL for Male) and by IBD subgroup (ulcerative colitis [UC] or Crohn's disease [CD]). Subjects who are re-screened will have their re-screen Hb substituted in lieu of screening Hb for purposes of determining the strata for randomization.

Protocol amendment 7.0 updated the study duration from 52 weeks to 12 weeks. For subjects who entered the study under the previous protocol for the 52 weeks open-label design and completed their study beyond the 12 weeks treatment period, the next scheduled visit will be their End of Study Visit. Otherwise, subjects after the eligibility screening period will enter a 12 weeks treatment period.

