6.3 Strata and Covariates

Randomization will employ screening Hb (< 10g/dL or ≥ 10g/dL for Females; < 11g/dL or ≥ 11g/dL for Males) and IBD subgroup (UC or CD) as binary stratification factors. Unless otherwise indicated, IBD subgroup will be included as a binary stratification factor and baseline Hb will be included as a continuous factor in statistical modelling.

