9.1 Primary Efficacy Analyses

9.1.1 Primary Analysis

Haemoglobin (Hb) concentration will be collected at screening (Visit 1), pre-randomization at Visit 2 (baseline assessment), and at each visit over the Treatment Period. Hb concentration (Observed Cases [OC]) will be summarised for the ITT and PP populations using descriptive statistics by visit for each treatment arm and overall. A scatterplot of Hb concentrations (OC) at Week 12 versus baseline will be presented by treatment arm for the ITT and PP populations.

A dichotomous variable, representing response status in the degree to which Hb increases relative to baseline, will be calculated for each visit over the Treatment Period. Those subjects with at least 2g/dL increase in Hb from baseline or who

have normalization of Hb (>12.0 g/dL for women, >13.0 g/dL for men) will be classified as "Hb responders".

The null hypothesis for the primary efficacy endpoint analysis is that the proportion of Hb responders at Week 12 in the ferric maltol treatment arm is at least 20% lower than the proportion of Hb responders at Week 12 in the IV Iron treatment arm (i.e., ferric maltol is inferior to IV Iron for rate of Hb response at Week 12). The alternative hypothesis is that the proportion of Hb responders at Week 12 in the ferric maltol treatment arm is not worse than 20% lower than the proportion of Hb responders at Week 12 in the IV Iron treatment arm (i.e., ferric maltol is non-inferior to IV Iron for rate of Hb response at Week 12).

The proportion of Hb responders at Week 12 will be compared between the two treatment arms, by calculating a 2-sided confidence interval for difference in the proportions of Hb responders (risk difference) between the two treatment arms and comparing the lower confidence limit of this CI to the pre-specified non-inferiority margin. The CI will be calculated using the Delta Method approach [1] based on a logistic regression model, adjusted for treatment arm, baseline Hb (below the observed median or at least the observed median), and IBD subgroup (UC or CD).

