9.2.1.2 Other Secondary Efficacy Endpoints

The analysis for the key secondary endpoint, CFB in Hb concentration at Week 12 (MI), will be repeated for the secondary endpoints: CFB in Hb concentration at Week 12 (MI) in subjects with baseline Hb <9.5 g/dL; CFB in Hb concentration at Week 4 (MI); and, CFB in Hb concentration at Week 4 (MI) in subjects with a baseline Hb <9.5 g/dL.

Two dichotomous variables, each representing response for the magnitude rise in Hb from baseline, will be calculated for each visit during the Treatment Period from the Hb concentration data. Those subjects with a rise in Hb from baseline of at least 1g/dL will be classified as "Hb rise responders" for the first variable; those subjects with a rise in Hb from baseline of at least 2g/dL will be classified as "Hb rise responders" for the second variable. Separate logistic regression models will be fitted to each of the Hb rise responders at Week 12 variables (secondary endpoints) using an MI approach for the ITT populations. Each model will include terms for the effects of treatment, baseline Hb (below the observed median or at least the observed median), and IBD subgroup. A hypothesis test of the null hypothesis of inferiority for ferric maltol responder rate compared to IV Iron responder rate will be considered for each Hb rise responder secondary endpoint using a non-inferiority margin of 20%. No formal statistical significance level to declare non-inferiority (i.e., rejection of the null hypothesis) of ferric maltol to IV Iron is defined, as CIs and p-values will be presented for descriptive purposes only. The p-value in testing the aforementioned hypotheses will be calculated as described in the primary analysis ([Section 9.1.1](#)).

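### The Hb-change ANCOVA splits baseline Hb at the observed median instead of using the continuous default of section 6.3, which costs some precision and leaves the adjustment in the Hb <9.5 g/dL subgroup undefined

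*SAP*

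**What the plan says.** SAP v3.0 section 6.3 sets the general rule: "Unless otherwise indicated, IBD subgroup will be included as a binary stratification factor and baseline Hb will be included as a continuous factor". Section 9.2.1.1 then states its own form for the ANCOVA of Hb change: "The ANCOVA model will have terms for treatment arm, baseline Hb (below the observed median or at least the observed median), and IBD subgroup". The code agrees with that text: PROC REG and the matching MIANALYZE step both use a variable named binarybaselineHb.

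Section 9.2.1.2 repeats this ANCOVA for Week 4 and for the low-Hb subgroup, including "CFB in Hb concentration at Week 12 (MI) in subjects with baseline Hb <9.5 g/dL", which section 2.3.2 lists among the key secondary endpoints. The post hoc analysis plan that follows v3.0 keeps the same model text (9.2.1.1, 9.2.1.2) and the same code (section 7).

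The primary logistic model in 9.1.1 is also "adjusted for treatment arm, baseline Hb (below the observed median or at least the observed median), and IBD subgroup (UC or CD"). In v3.0 the repeated-measures model of 9.1.2.2 names baseline Hb without a cut, so the default applies there; the post hoc plan introduces the cut in that model too.

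The Hb strata used for randomisation are sex-specific and based on screening values: "Randomization will employ screening Hb (< 10g/dL or ≥ 10g/dL for Females; < 11g/dL or ≥ 11g/dL for Males").

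**The concern.** Baseline Hb is measured as a number and is already in the imputed dataset, because the code subtracts it from Week 12 Hb to form the change. Change from baseline is usually correlated with baseline, so this is the covariate most likely to reduce residual variance. Replacing it with an above/below indicator, at one median for both sexes, gives part of that reduction away.

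The subgroup raises a separate question. A cut point computed from the whole trial may lie above every value in a subgroup defined by low Hb. At stake are the width of the confidence interval for a key secondary estimate, and whether two programmers following the plan would fit the same model in the subgroup.

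**Working it through.** **The plan's own figure.** The only related calculation in the SAP is the sample size in section 4, and it uses no covariate. With 75% response in both arms, margin 20%, one-sided 0.025 and 90% power, the unpooled formula gives (1.960 + 1.282)² × 2 × 0.75 × 0.25 / 0.20² = 98.5 per arm. With a continuity correction this becomes 108.3, against 108 stated. Then 108 × 1.12 = 120.96, that is 121. The present point does not touch this figure.

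**Cost of the split for Hb change.** Inputs: N = 242 (section 3.1). The SAP gives no Hb SD and no baseline to Week 12 correlation r, so equal SDs and r = 0.3, 0.5 and 0.7 are assumptions.

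1. With equal SDs, the squared correlation of baseline with change is R² = (1 − r)/2, that is 0.35, 0.25 and 0.15.
2. A median split of a normal covariate retains 2/π = 0.637 of R² and loses 0.363.
3. Variance ratio, split to continuous = (1 − 0.637 R²)/(1 − R²). The confidence interval width scales with its square root, and the equivalent sample size is 242 divided by the ratio.

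| r | R² | Variance ratio | CI wider by | Equivalent N | Simulated ratio |
|---|---|---|---|---|---|
| 0.3 | 0.35 | 0.777/0.65 = 1.20 | 9% | 202 | 1.19 |
| 0.5 | 0.25 | 0.841/0.75 = 1.12 | 6% | 216 | 1.11 |
| 0.7 | 0.15 | 0.905/0.85 = 1.06 | 3% | 227 | 1.07 |

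The last column comes from 4,000 simulated trials of 242 subjects per setting (assumed overall mean baseline Hb 10.5 g/dL, within-sex SD 1, sexes 0.8 g/dL apart). In the same runs, dropping baseline Hb altogether gave ratios of 1.56, 1.33 and 1.18, so the split recovers much of the gain but not all of it.

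**Subgroup with baseline Hb <9.5 g/dL.** Let M be the median used for the cut.

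- If M is the whole-trial median and M ≥ 9.5, every subject in the subgroup is below M. The indicator is constant, aliased with the intercept, and adjusts for nothing.
- With N = 242 and assumed SDs of 0.8 to 1.3, this happens in about 100% of simulated trials when mean baseline Hb is 9.8 or more, about 50% at 9.5, and 0% to 4% at 9.3 or less.
- If M is recomputed within the subgroup, the indicator varies and is usable.

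Assuming mean baseline Hb of 10.2 or 10.6, SD 1 and r from 0.7 to 0.3, having no covariate raises subgroup variance by 3% to 13% over continuous baseline Hb (interval about 2% to 6% wider, from √1.034 and √1.127). A within-subgroup median raises it by 1.5% to 5%.

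**The case against.** Section 6.3 opens with an exception clause, and the ANCOVA uses it openly, with text and code in agreement. A reader might infer that the plan contradicts itself; it does not. What remains is a choice that costs precision.

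The consequence is also limited. Randomisation keeps the treatment estimate unbiased, and 9.2.1.1 sets no formal significance level, treating the p-value as descriptive. A reader might infer that the primary non-inferiority decision is at risk because 9.1.1 uses the same split. The check does not support this: simulations of 242 subjects under assumed scenarios gave a variance ratio of 0.98 to 1.02 for the risk difference, even against a model with continuous Hb plus sex.

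It is also tempting to say that the <9.5 g/dL subgroup has no usable covariate. That needs a whole-trial median of at least 9.5 g/dL. Strata cut at 10 and 11 g/dL make such a median plausible, but the SAP states neither its value nor its source population.

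Finally, the mismatch with the sex-specific strata is not itself the source of the loss. In the simulation above, a binary indicator at the 10/11 g/dL cuts, applied to baseline Hb, did slightly worse than the median split (variance ratios 1.30, 1.17 and 1.08). The loss comes from dichotomising.

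All of this limits the weight of the point. None of it gives a reason to prefer the split for Hb change.

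**Conclusion.** The point holds as one of efficiency and specification. The median split in the Hb-change ANCOVA discards about 36% of the variance that baseline Hb could explain. That makes the variance of the treatment difference about 6% to 20% larger and its confidence interval about 3% to 9% wider, for assumed correlations of 0.7 to 0.3 with equal SDs and a roughly normal baseline. In the <9.5 g/dL subgroup the plan leaves open which population supplies the median, and under one plausible reading the baseline term drops out. There is no bias, and the primary conclusion is essentially unaffected.

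**What to change.** In the Hb-change ANCOVAs (Week 12, Week 4 and both <9.5 g/dL repeats) use continuous baseline Hb, as in section 6.3, together with treatment arm and IBD subgroup. Sex or the sex-specific randomisation stratum may be added but is not needed for this purpose. Change binarybaselineHb to baselineHb in the PROC REG model statement and in the matching MIANALYZE effects list. This also gives the <9.5 g/dL subgroup a covariate that varies, so the median's source population no longer matters there. If the split is kept, state the population in which the median is taken and how the subgroup is adjusted.

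The primary logistic model need not change. For the analysis already reported, show the continuous-covariate ANCOVA beside the pre-specified one, labelled post hoc, rather than replacing it. The cost is a few lines of text and code; no new data are needed.

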7.1.2 Non-Date Values

Every effort will be made to obtain required data at each scheduled evaluation from all subjects who have been enrolled. Missing values for the primary efficacy endpoint of Hb responder (i.e., a subject who either has at least 2g/dL rise in Hb from baseline or has shift from baseline of anaemic to non-anaemic status) at Week 12 will be imputed using a Multiple imputation approach for the primary efficacy analysis on the ITT population. If the value of Hb is missing, multiple imputation based on pre-treatment visits will be used in the baseline and multiple imputation based on post-treatment visits will be used to determine the post-baseline value to be used in the primary efficacy endpoint analysis on the ITT population.

As additional sensitivity analyses, missing values for the primary efficacy endpoint on the ITT population will also be imputed using a Last Observation Carried Forward (LOCF) approach up to Week 12.

Missing values for efficacy variables will be replaced for the secondary endpoint analyses, as follows:

- For the key endpoint, 'Hb concentration within normal limits', subjects not returning to a follow-up visit will be assumed to have Hb concentration not within normal limits.
- For the endpoint, 'Increases in Hb concentration of $\geq 1\text{g/dL}$ ', subjects not returning to a follow-up visit will have their Hb concentration imputed using multiple imputation.
- For the endpoint, 'Increases in Hb concentration of $\geq 2\text{g/dL}$ ', subjects not returning to a follow-up visit will have their Hb concentration imputed using multiple imputation.

Missing values for the long-term secondary efficacy endpoints, normalization of Hb at 6 and 12 months and normalization of ferritin at 6 and 12 months, will not be imputed.

Missing values for the SF-36 pharmacoeconomic analysis will be imputed by a LOCF approach up to Week 12. Missing values for all other pharmacoeconomic analyses will be kept as missing.

Safety data will be used according to availability, with no imputation for missing data.

Imputation of data values will only be carried out, where indicated, for computational purposes and fitting of models. Actual data values, as they appear in the original CRFs, will be shown in the data listings.

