Note that missing values for the Hb responder status at Week 12 primary efficacy analysis will be imputed using a multiple imputation approach for ITT population. BOCF will be used in the case of missing baseline data to use the screening value. Missing values of Hb concentration at Week 12 will be imputed using the SAS[®] procedure MI. This will generate 20 complete datasets containing imputed values of Hb concentration at Week 12 for those missing in the original dataset. Variables considered helpful in guiding this imputation are baseline (Visit 2) Hb concentration and treatment arm. The code for implementing the SAS[®] procedure MI is:

```
PROC MI DATA = <dataset _name> NIMPUTE = 20 SEED = <seed> OUT = MI_out;  
  VAR baselineHb TreatmentArm Week12Hb;  
  EM MAXITER = 10000;  
RUN;
```

Each model, corresponding to a given endpoint analysis, will be fitted against each of the imputed datasets. The SAS[®] procedure MIANALYZE will then be used to combine the individual analysis results for the given endpoint into one result.

The null hypothesis for the primary efficacy analysis will be rejected (i.e., ferric maltol will be deemed non-inferior to IV Iron), if the LCL of the 95% CI for the difference (ferric maltol - IV Iron) in proportions of Hb responders at Week 12 (BOCF) is $\geq -20\%$ for both the ITT analysis and the PP analysis. The p-value in testing the aforementioned hypotheses will be equal to one minus the confidence coefficient corresponding to the CI for the risk difference whose LCL equals -20% (i.e., inverting the CI for the risk difference to a test statistic and calculating the p-value from the test statistic).

The proportion of Hb responders will be summarised for the ITT and PP populations using descriptive statistics by visit over the Treatment Period for each treatment

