7 DATA HANDLING METHODS

For details of the data handling methods, refer to Statistical Analysis Plan v3.0, dated 14 February 2019.

Missing data for adherence to ferric maltol (i.e. no returned bottles and no pill count) will not be imputed and will not be assumed to be zero adherence or all tablets taken.

The code for implementing the SAS® procedure MI is:

```
PROC MI DATA = <dataset _name> NIMPUTE = 20 SEED = <seed> OUT = MI_out;  
  VAR baselineHbtrans gender ibd Week4Hbtrans Week12Hbtrans;  
  EM MAXITER = 10000;  
RUN;
```

For the multiple imputation, the code for implementing the SAS® procedure MIANALYZE to the CFB Hb concentration at Week 12 secondary endpoint is:

```
DATA CFB_Impute; SET MI_out; CFBHbW12 = Week12Hb - baselineHb; RUN;  
  
PROC SORT DATA = CFB_Impute; BY _Imputation_; RUN;  
  
PROC REG DATA = CFB_Impute OUTEST = outreg COVOUT;  
  BY _Imputation_;  
  MODEL CFBHbW12 = binarybaselineHb TreatmentArm IBDGroup;  
RUN;  
  
PROC MIANALYZE DATA = outreg EDF = <complete-data degrees of freedom>;  
  MODELEFFECTS Intercept binarybaselineHb TreatmentArm IBDGroup;  
  ODS OUTPUT ParameterEstimates = parm1;  
RUN;
```

The code for implementing the SAS® procedure MIANALYZE to the Hb normal limit responder at Week 12 secondary endpoint for the ITT population is:

```
DATA NormalHb_Impute; SET MI_out;  
  NLResponder = 0;  
  IF Gender = 'F' AND Week12Hb => 12.0 THEN NLResponder = 1;  
  IF Gender = 'M' AND Week12Hb => 13.0 THEN NLResponder = 1;  
RUN;  
  
PROC SORT DATA = NormalHb_Impute; BY _Imputation_; RUN;  
  
PROC LOGISTIC DATA = NormalHb_Impute;  
  MODEL NLResponder = binarybaselineHb TreatmentArm IBDGroup / covb;  
  BY _Imputation_;  
  ODS OUTPUT ParameterEstimates = lgsparms  
               CovB              = lgscovb;  
RUN;  
  
PROC MIANALYZE PARMS = lgsparms COVB(effectvar=stacking) = lgscovb;  
  MODELEFFECTS Intercept binarybaselineHb TreatmentArm IBDGroup;  
RUN
```

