The proportion of Hb responders at Week 12 will be compared between the two treatment arms, by calculating a 2-sided confidence interval for difference in the proportions of Hb responders (risk difference) between the two treatment arms and comparing the lower confidence limit of this CI to the pre-specified non-inferiority margin. The CI will be calculated using the Delta Method approach [1] based on a logistic regression model, adjusted for treatment arm, baseline Hb (below the observed median or at least the observed median), and IBD subgroup (UC or CD). Note: For the CI calculation in the primary efficacy endpoint, the risk difference model was applied in the original analysis for CSR v1.0. The analysis method will be corrected to the Delta Method approach in the current post hoc analysis.

Post-hoc change: Note that missing values for the Hb responder status at Week 12 primary efficacy analysis will be imputed using a multiple imputation (MI) approach for ITT population. Missing values of Hb concentration at Week 12 will be imputed using the SAS[®] procedure MI. This will generate 20 complete datasets containing imputed values of Hb concentration at Week 12 for those missing in the original dataset. Variables considered helpful in guiding this imputation are deviation of baseline (Visit 2) Hb concentration from response threshold, deviation of Week 4 Hb concentration from response threshold, gender and IBD subgroup. A separate model will be computed for each treatment arm.

The Week 12 imputed value will then be back transformed from the Week 12 deviation from the response threshold.

Each model, corresponding to a given endpoint analysis, will be fitted against each of the imputed datasets. The SAS[®] procedure MIANALYZE will then be used to combine the individual analysis results for the given endpoint into one result.

The null hypothesis for the primary efficacy analysis will be rejected (i.e., ferric maltol will be deemed non-inferior to IV Iron), if the LCL of the 95% CI for the

difference (ferric maltol – IV Iron) in proportions of Hb responders at Week 12 is $\geq -20\%$ for both the ITT analysis and the re-evaluated PP analysis. The p-value in testing the aforementioned hypotheses will be equal to one minus the confidence coefficient corresponding to the CI for the risk difference whose LCL equals -20% (i.e., inverting the CI for the risk difference to a test statistic and calculating the p-value from the test statistic).

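### Week 12 Hb normalisation (secondary, ITT) has two incompatible missing-data rules, non-responder and multiple imputation, and its printed code needs repair

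*SAP*

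**What the plan says.** There are two plans in the file: SAP v3.0, and a later SAP for revised and post-hoc analyses (the post-hoc SAP), which refers back to v3.0 for data handling.

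**Non-responder rule.** v3.0 section 7.1.2 says of the normal-limits endpoint: "subjects not returning to a follow-up visit will be assumed to have Hb concentration not within normal limits". Its next two bullets assign multiple imputation to the endpoints of a rise of at least 1 and at least 2 g/dL. Section 9.2.1.1 repeats the non-responder rule for Week 12: "Subjects missing Hb concentration at Week 12 will be assumed to have Hb concentration not within normal limits". Post-hoc SAP 9.2.1.1 keeps that sentence.

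**Multiple imputation.** The same v3.0 section 9.2.1.1 continues: "The summary will also present the Hb normal limit responder rate for the Week 12 visit (MI) for ITT population using descriptive statistics". The odds ratio carries the same label, and post-hoc SAP 9.2.1.1 repeats both. The v3.0 code begins "DATA NormalHb_Impute; SET MI_out" and pools with PROC MIANALYZE. Section 9.1.1 describes that input: "This will generate 20 complete datasets containing imputed values of Hb concentration at Week 12 for those missing in the original dataset".

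**Code.** Both plans print "MODEL NLResponder = binarybaselineHb TreatmentArm IBDGroup / covb", with no EVENT=, REF= or DESCENDING option. In post-hoc SAP section 7, PROC MI imputes `Week12Hbtrans`, while the responder step reads `Week12Hb`. Post-hoc SAP 9.1.1 adds in words that the imputed value is back-transformed, and that "A separate model will be computed for each treatment arm".

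**The concern.** Counting a missing value as failure and imputing it from observed Hb estimate different quantities. v3.0 9.2.1.1 repeats the primary hypothesis test for this endpoint, including the 20-point margin. The statement that p-values are descriptive only is attached to the change-from-baseline analysis (9.2.1.1) and the rise responders (9.2.1.2), not to this endpoint. The plan therefore allows two different risk differences to be set against one margin, and the choice between them could be made after the data are seen. The clash extends to the normal-limits endpoints at Week 4 and in subjects with baseline Hb below 9.5 g/dL, because 9.2.1.2 repeats the Week 12 analysis for them.

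**Working it through.** **1. Can the two rules be separated by population?** No. v3.0 section 5.4 removes subjects with no Week 12 Hb from the PP population, so both rules fall on the same ITT subjects.

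**2. Which rule does the code apply?** In v3.0, `MI_out` holds completed Week 12 values, so no subject is missing when `NLResponder` is derived, and the non-responder rule never operates. In the post-hoc SAP the result depends on the back-transformation. With it, the code gives MI. Without it, `Week12Hb` stays missing, SAS treats it as below the cut-off, and the subject scores 0.

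**3. Inputs from the plan.** v3.0 section 4 gives a 75% response rate in both arms, a 20-point margin, a 2-sided 95% interval, 90% power, and 108 inflated to 121 per arm. These figures reproduce:

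- n = 2(0.75)(0.25)(1.960 + 1.282)²/0.20² = 98.5
- with continuity correction, (98.5/4)[1 + √(1 + 4/(98.5 × 0.20))]² = 108.3
- 108 × 1.12 = 120.96, so 121

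They concern the primary endpoint and are not in question; only N = 121 per arm is used below.

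**4. Size of the gap.** The plan states neither missing rates nor normalisation rates, so both are assumptions. Let pF and pI be the true normalisation rates (ferric maltol, IV iron) and mF and mI the missing proportions, with missing subjects like the observed ones in their arm. Unadjusted:

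- MI: difference = pF − pI; SE² = pF(1 − pF)/[N(1 − mF)] + pI(1 − pI)/[N(1 − mI)].
- Non-responder: a = pF(1 − mF), b = pI(1 − mI); difference = a − b; SE² = [a(1 − a) + b(1 − b)]/N.
- Lower limit = difference − 1.96 SE.

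| pF / pI | mF / mI | MI: difference (lower limit) | Non-responder: difference (lower limit) | Shift |
|---|---|---|---|---|
| 70% / 70% | 12% / 12% | 0.0 (−12.3) | 0.0 (−12.3) | 0.0 |
| 70% / 70% | 15% / 5% | 0.0 (−12.2) | −7.0 (−19.1) | −7.0 |
| 70% / 70% | 5% / 15% | 0.0 (−12.2) | +7.0 (−5.1) | +7.0 |
| 65% / 70% | 12% / 12% | −5.0 (−17.6) | −4.4 (−16.8) | +0.6 |
| 65% / 70% | 15% / 5% | −5.0 (−17.5) | −11.25 (−23.5) | −6.25 |
| 65% / 70% | 5% / 15% | −5.0 (−17.4) | +2.25 (−10.1) | +7.25 |
| 60% / 70% | 12% / 12% | −10.0 (−22.7) | −8.8 (−21.2) | +1.2 |
| 60% / 70% | 15% / 5% | −10.0 (−22.6) | −15.5 (−27.8) | −5.5 |
| 60% / 70% | 5% / 15% | −10.0 (−22.6) | −2.5 (−14.9) | +7.5 |

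With equal missingness m, the shift is m × \|pF − pI\| towards zero. With equal true rates p and a 10-point gap in missingness, it is 10p: 6 points at 60% and 7 points at 70%. The two rules fall on opposite sides of −20 in the fifth row (MI passes, non-responder fails) and in the last row (the reverse).

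**5. Event direction.** PROC LOGISTIC models the lower ordered value of a 0/1 response by default, here non-response. At 65% v 70% the intended odds ratio is (0.65/0.35)/(0.70/0.30) = 0.80. The printed statement gives 1/0.796 = 1.26.

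**The case against.** The best defence concerns reach. v3.0 section 2.3.2 lists this endpoint among the other secondary endpoints, although 7.1.2 and 9.2.1.2 call it key. It does not enter the primary decision rule, and PP is untouched. v3.0 had already been run for CSR v1.0, so mainly the post-hoc SAP can still be changed. All of that stands, and it limits the weight of the point. It does not reconcile the two rules.

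A reader might also infer more than the documents support:

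- **That the event coding explains the two results.** It does not. It is a separate defect that reverses direction and leaves the size on the logit scale unchanged.
- **That the sign of the risk difference is certainly reversed.** The printed code outputs only coefficients and covariances; the Delta Method step is not printed. The text asks for responder proportions and shows rates by arm, so a reversed sign would be noticeable. Only the inverted odds ratio follows from the code as printed.
- **That the primary rule has the same clash**, because v3.0 9.1.1 states it as the difference "in proportions of Hb responders at Week 12 (BOCF". That section also uses BOCF for replacing a missing baseline by the screening value, and assigns MI to missing Week 12 Hb. The tag is probably loose wording, and post-hoc SAP 9.1.1 no longer has it.
- **That the post-hoc imputation method contradicts itself.** The text states both the per-arm model and the back-transformation, and the dataset name in PROC MI is a placeholder that allows one run per arm. The code is incomplete rather than opposed to the text.
- **That the non-responder rule always counts against ferric maltol.** The direction depends on which arm has more missing data, which the plan does not say.

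**Conclusion.** The contradiction is real and unresolved in both plans: one ITT secondary endpoint has two missing-data rules, and the v3.0 code applies the one that the text of 7.1.2 does not assign to it. Under the assumed 60% to 70% normalisation, with missing subjects like the observed ones, the gap is about 1 point or less with equal missingness. It is about 6 to 7 points, in either direction, with a 10-point imbalance (5.5 to 7.5 in the unequal rows tabulated). That is roughly a third of the margin and can change the verdict against it. These sizes are illustrations, not estimates for this trial. The primary non-inferiority conclusion is not affected. The missing event option inverts the odds ratio under the software default. The gaps in the post-hoc code and the (BOCF) tag are matters of alignment and wording.

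**What to change.** - **One rule.** State it identically in v3.0 7.1.2 and 9.2.1.1 and in post-hoc SAP 9.2.1.1. Since 7.1.2 gives this endpoint non-responder imputation and the rise endpoints MI, make non-responder imputation the main analysis and relabel MI as a named sensitivity analysis. The reverse is also acceptable if stated once. Carry the choice to the Week 4 and baseline Hb below 9.5 g/dL versions.
- **Logistic code, wherever kept.** Write `MODEL NLResponder(EVENT='1') = ...`.
- **Post-hoc SAP code only.** Run PROC MI separately by arm, and back-transform `Week12Hbtrans` to `Week12Hb` before deriving responders. Do not split by arm in v3.0, where treatment arm is itself an imputation variable.
- **Risk difference.** Where MI is used, compute the Delta Method difference and its variance in each imputed dataset, and pool those.
- **Wording.** Correct the (BOCF) tag in the v3.0 decision rule.

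The cost is text and code edits plus a rerun of the affected tables; no new data are needed.
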